### 5.2.2 Informed Consent

The Investigator or his/her authorized designee will conduct the Informed Consent process, as required by applicable regulations and the center's EC. This process will include a verbal discussion with the subject on all aspects of the clinical investigation that are relevant to the subject's decision to participate, such as details of clinical investigation procedures, anticipated benefits, and potential risks of clinical investigation participation. Subjects must be informed about their right to withdraw from the clinical investigation at any time and for any reason without sanction, penalty or loss of benefits to which the subject is otherwise entitled. Withdrawal from the clinical investigation will not jeopardize their future medical care or relationship with the investigator.

During the discussion, the Principal Investigator or his/her authorized designee will avoid any improper influence on the subject and will respect subject's legal rights. The subject shall be provided with the Informed Consent form written in a language that is understandable to the subject and has been approved by the center's EC. The subject shall have adequate time to review, ask questions and consider participation. The Principal Investigator or his/her authorized designee will make efforts to ensure that the

## Clinical Investigation Plan

subject understands the information provided. If the subject agrees to participate, the Informed Consent form must be signed and dated by the subject and thereafter by the person obtaining the consent prior to any clinical investigation-specific procedures. The signed original will be filed in the subject's hospital or research charts, and a copy will be provided to the subject.

Failure to obtain informed consent from a subject prior to clinical investigation enrollment should be reported to Sponsor within 5 working days and to the reviewing center's EC according to the EC's reporting requirements.

If, during the clinical investigation, new information becomes available that can significantly affect a subject's future health and medical care, the Principal Investigator or his/her authorized designee will provide this information to the subject. If relevant, the subject will be asked to confirm their continuing informed consent in writing.

### 5.2.2.1 Vulnerable Populations

Vulnerable patients are defined as patients whose willingness to volunteer in a clinical investigation could be unduly influenced by the expectation, whether justified or not, of benefits associated with participation or of retaliatory response from senior members of a hierarchy in case of refusal to participate. Examples of populations which may contain vulnerable patients include: Individuals with lack of or loss of autonomy due to immaturity or through mental disability, persons in nursing homes, children, impoverished persons, subjects in emergency situations, ethnic minority groups, homeless persons, nomads, refugees, and those incapable of giving informed consent. Other vulnerable patients include, for example, members of a group with a hierarchical structure such as university students, subordinate hospital and laboratory personnel, employees of the sponsor, members of the armed forces, and persons kept in detention.

This clinical investigation will not permit enrollment of patients from vulnerable populations identified in ISO Standards 14155.

## 5.3 Eligibility Criteria

### 5.3.1 General Eligibility Criteria

Assessment for general eligibility criteria is based on medical records of the site and interview with a candidate patient. If some of the clinical and laboratory tests are not included in site standard tests, they must be done but after written Informed Consent is obtained. Patients must meet ALL of the inclusion criteria to be considered for the clinical investigation. If ANY of the exclusion criteria are met, the patient is excluded from the clinical investigation and cannot be enrolled.

### 5.3.2 Inclusion Criteria

#### 5.3.2.1 Inclusion Criteria - High Risk Cohort

Candidates for High Risk classification must meet all the following inclusion criteria:

1. Subjects must have co-morbidities such that the local heart team concur the predicted risk of operative mortality is  $\geq 15\%$  or a minimum STS score of 8%.

## Clinical Investigation Plan

A candidate who does not meet the STS score criteria of  $\geq 8\%$  may be included in the study if at least one surgeon in the local heart team concludes and documents the patient's predicted risk of operative mortality is  $\geq 15\%$ . The surgeon's assessment of operative comorbidities (including frailty indices) not captured by the STS score must be documented in the study case report form as well as in the patient medical record.

2. Subject is of legal age or older for consent in the host country.
3. Subject has senile degenerative aortic valve stenosis with echo-derived criteria: mean gradient  $>40$  mmHg or jet velocity greater than 4.0 m/s or doppler velocity index (DVI)  $<0.25$  and an initial aortic valve area (AVA) of  $\leq 1.0$  cm $^2$  (indexed EOA  $\leq 0.6$  cm $^2$ /m $^2$ ). (Qualifying AVA baseline measurement must be within 60 days prior to informed consent).
4. Subject has symptomatic aortic stenosis as demonstrated by NYHA Functional Classification of II, III, or IV.
5. The subject has been informed of the nature of the study, agrees to its provisions and has provided written informed consent as approved by the Ethics Committee (EC) of the respective clinical site.
6. The subject and the treating physician agree that the subject will return for all required post-procedure follow-up visits.
7. Subject's aortic annulus is 19-27mm diameter as measured by CT conducted within 12 months prior to informed consent. If a CT is contraindicated and/or not possible to be obtained for certain subjects, a 3D echo and non-contrast CT of chest and abdomen/pelvis may be accepted.

### 5.3.2.2 Inclusion Criteria - Extreme Risk Cohort:

All candidates for Extreme Risk classification must meet # 2, 3, 4, 5, 6, 7 of the above criteria, and

1. After formal consultation with the local heart team (including at least one surgeon) it is agreed that medical factors preclude the subject from undergoing operation, based on a conclusion that the probability of death or serious, irreversible morbidity exceeds the probability of meaningful improvement. Specifically, the probability of death or serious, irreversible morbidity should exceed 50%. The local heart teams' consult notes shall specify the medical or anatomic factors leading to that conclusion and include a printout of the calculation of the STS score to additionally identify the risks in these patients.

### 5.3.3 Exclusion Criteria - High and Extreme Risk Cohort

Candidates will be excluded if any of the following conditions are present:

1. Evidence of an acute myocardial infarction (defined as: ST Segment Elevation as evidenced on 12 Lead ECG) within 30 days prior to index procedure.
2. Aortic valve is a congenital unicuspид or congenital bicuspid valve, or is non-calcified as verified by echocardiography.
3. Mixed aortic valve disease (aortic stenosis and aortic regurgitation with predominant aortic regurgitation 3-4+).

## Clinical Investigation Plan

4. Any percutaneous coronary or peripheral interventional procedure performed within 30 days prior to index procedure.
5. Pre-existing prosthetic heart valve or other implant in any valve position, prosthetic ring, severe circumferential mitral annular calcification (MAC) which is continuous with calcium in the LVOT, severe (greater than 3+) mitral insufficiency, or severe mitral stenosis with pulmonary compromise.
6. Blood dyscrasias as defined: leukopenia (WBC<3000 mm^3), acute anemia (Hb < 9 g/dL), thrombocytopenia (platelet count <50,000 cells/mm^3).
7. History of bleeding diathesis or coagulopathy.
8. Cardiogenic shock manifested by low cardiac output, vasopressor dependence, or mechanical hemodynamic support.
9. Untreated clinically significant coronary artery disease requiring revascularization.
10. Hemodynamic instability requiring inotropic support or mechanical heart assistance.
11. Need for emergency surgery for any reason.
12. Hypertrophic cardiomyopathy with or without obstruction (HOCM).
13. Severe ventricular dysfunction with LVEF <20% as measured by resting echocardiogram.
14. Echocardiographic evidence of intracardiac mass, thrombus or vegetation.
15. Active peptic ulcer or upper GI bleeding within 3 months prior to index procedure.
16. A known hypersensitivity or contraindication to aspirin, heparin, ticlopidine (Ticlid), or clopidogrel (Plavix), or sensitivity to contrast media which cannot be adequately premedicated.
17. Recent (within 6 months prior to index procedure date) cerebrovascular accident (CVA) or a transient ischemic attack (TIA).
18. Renal insufficiency (creatinine > 3.0 mg/dL) and/or end stage renal disease requiring chronic dialysis.
19. Life expectancy < 12 months from the time of informed consent due to non-cardiac co-morbid conditions.
20. Significant aortic disease, including abdominal aortic or thoracic aneurysm defined as maximal luminal diameter 5cm or greater; marked tortuosity (hyper acute bend), aortic arch atheroma (especially if thick [> 5 mm], protruding or ulcerated) or narrowing (especially with calcification and surface irregularities) of the abdominal or thoracic aorta, severe “unfolding” and tortuosity of the thoracic aorta.
21. Native aortic annulus size < 19 mm or > 27 mm per the baseline diagnostic imaging.
22. Aortic root angulation > 70°.
23. Currently participating in an investigational drug or device study.
24. Active bacterial endocarditis within 6 months prior to the index procedure.
25. Bulky calcified aortic valve leaflets in close proximity to coronary ostia.
26. Non-calcified aortic annulus.

## Clinical Investigation Plan

27. Iliofemoral vessel characteristics that would preclude safe insertion of the FlexNav™ delivery system with or without an arterial introducer sheath such as severe obstructive calcification, or severe tortuosity.
28. In the judgment of the investigator, a condition that could limit a patient's ability or willingness to participate in the study, comply with study required testing and/or follow-up visits or that could impact scientific integrity of the study

### 5.4 Subject Enrollment

A patient will be considered enrolled in the study after completion of all of the following steps:

1. Signed informed consent is obtained.
2. Based on the screening assessments, it is determined that the subject meets all of the inclusion and none of the exclusion criteria.
3. Subject is approved by the Subject Selection Committee.
4. Portico implant attempt defined as insertion of the FlexNav™ Delivery System into the subject's vasculature.

The following terms will be used to describe potential study subjects:

- **Screen Failure:** Consented subjects who undergo study-specific testing and are found to have met exclusion criteria or not all inclusion criteria. Additionally, if a site disagrees with the Subject Selection Committee's final decision regarding risk classification the subject will not be eligible for enrollment in the study and will be considered a screen failure.
- **Pre-procedural Exclusion:** Consented subjects who undergo study-specific testing and meet study criteria but do not undergo a Portico implant attempt will not be considered enrolled and will be exited from the study without further follow up.
- **Enrolled:** These subjects will be considered enrolled in the study and will fall into one of the following categories:
  - **Attempted-to-Treat:** Subjects who undergo a Portico implant attempt but do not have a Portico valve implanted will be followed for 30 days post procedure for adverse events and then formally withdrawn from the study
  - **Implanted:** Subjects who have a Portico valve implanted will be followed according to the clinical investigation and will be included in the analysis population.
  - **CIP Deviations:** Subjects who have a Portico valve implanted and are later found to have met exclusion criteria or not all inclusion criteria. These subjects will be followed according to the clinical investigation and will be included in the analysis population.

Notification of enrollment to the Sponsor is considered to have occurred when the Sponsor has received the applicable CRF (Procedure Form).

To ensure enrollment balance across study sites, no investigational site will be permitted to enroll more than 20% of the analysis population.

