### 3.4.4 Adjudication of Adverse Events by an Independent Clinical Events Committee

An independent Clinical Events Committee (CEC), consisting of, at a minimum, an interventional cardiologist, cardiologist, cardiothoracic surgeon, and a neurologist will review and adjudicate pre-specified events reported by investigators or identified by Safety personnel in the clinical investigation as defined in the CEC Manual of Operations Charter. Events related to primary and descriptive endpoint criteria will be adjudicated according to the Valve Academic Research Consortium (VARC-2) definitions. The CEC will have final adjudication responsibilities for subject outcomes related to primary and descriptive outcome measures.

The same CEC used in the Portico US IDE pivotal trial will be utilized for this clinical investigation.

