## Clinical Investigation Plan

the right to withdraw at any time without penalty or loss of benefit. Conceivable reasons for discontinuation may include, but not be limited to, the following:

- Subject death
- Subject voluntary withdrawal
- Subject lost-to follow-up as described below
- Subject's follow-up is terminated according to [Section 3.5].

The Sponsor must be notified of the reason(s) for subject discontinuation. The site will provide this information to the Sponsor. Investigators must also report this to their respective EC as defined by their institution's procedure(s).

No additional follow-up will be required or data recorded from subjects once withdrawn from the clinical investigation, except for the status (deceased/alive if subject agrees).

However, if a subject withdraws from the investigation due to problems related to the safety or performance of the device under investigation, the investigator shall ask for the subject's permission to follow his/her status/condition outside of the clinical investigation.

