#### 6.5.2.1 30 Day Follow-Up

The 30-day follow-up visit will take place 30 days (-7/+21 days) post-index procedure, and will include the following assessments:

1. Physical exam (weight, heart rate, blood pressure)
2. Canadian Cardiovascular Society (CCS) Angina Scale Assessment
3. Modified Rankin Scale (mRS)

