### 6.5.3 Unscheduled Follow-up

#### 6.5.3.1 Unscheduled Follow-Up Visits for Evaluation of Suspected Neurological Event

If the subject experiences a neurological event (trans-ischemic attack (TIA), stroke, or encephalopathy), the event should be documented on an adverse event form and further evaluation should be performed at an unscheduled visit 90 days ( $\pm 14$  days) from the date of the neurological event. The unscheduled visit will include the following assessments:

- Neurological Assessment conducted by a neurologist or a neurology fellow
- Modified Rankin Score (mRS)
- NIH Stroke Scale

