## 7.3 Adverse Event and Device Deficiency Reporting

### 7.3.1 Adverse Event Reporting

Safety surveillance and reporting starts as soon as the patient is consented into the clinical investigation. Safety surveillance and reporting will continue until the last 12-month follow-up visit has been performed, the subject is deceased, the subject concludes participation in the clinical investigation or the subject withdraws from the clinical investigation. All adverse event data, including deaths and device deficiency data, will be collected throughout the time period defined above and will be reported to the Sponsor on a CRF. Additional information with regard to an adverse event should be updated within the appropriate CRF.

Unchanged, chronic, non-worsening or pre-existing conditions are not AEs and should not be reported.

Adverse event reporting will include:

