## Clinical Investigation Plan

ii. Hemorrhagic Stroke is defined as an acute symptomatic episode of focal or global cerebral or spinal dysfunction caused by a nontraumatic intraparenchymal, intraventricular, or subarachnoid hemorrhage.

Stroke Disability (consistent with VARC 2 Definitions):

- i. **Disabling:** an mRS score of 2 or more at 90 days and an increase of at least one mRS category from an individual's pre-stroke baseline
- ii. **Non-disabling:** an mRS score of < 2 at 90 days or one that does not result in an increase of at least one mRS category from an individual's pre-stroke baseline
- b. Cerebral Infarction: Evidence of brain cell death from imaging studies or pathological examination. If there are clinical symptoms, then it is a stroke; otherwise, it is an asymptomatic cerebral infarction.
- c. Transient Ischemic Attack (TIA): A transient (less than (<) 24 hrs) episode of neurological dysfunction caused by focal brain, spinal cord, or retinal ischemia, without acute infarction. No evidence of infarction if imaging performed.
- d. Encephalopathy: Altered mental state (e.g., seizures, delirium, confusion, hallucinations, dementia, coma, psychiatric episode, etc.).
- e. Intracranial Hemorrhage: Collection of blood between the brain and skull. Subcategorized as epidural, subdural, and subarachnoid bleeds.

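### The day-30 withdrawal of Attempted-to-Treat subjects conflicts with the 90-day mRS that classifies a stroke as disabling or non-disabling, and with the 12-month follow-up in section 3.3

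*Protocol*

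**What the plan says.** **Withdrawal.** Protocol 5.4 counts Attempted-to-Treat subjects as enrolled and says that they "will be followed for 30 days post procedure for adverse events and then formally withdrawn from the study". Section 6.2.3 repeats the rule, and 6.5.2 asks only for their 30-day visit. On its timing, 6.5.2.1 says: "The 30-day follow-up visit will take place 30 days (-7/+21 days) post-index procedure". Section 5.5 says "No additional follow-up will be required or data recorded from subjects once withdrawn from the clinical investigation", apart from vital status with the subject's agreement. Section 7.3.1 lists, among the points at which safety surveillance ends, that "the subject concludes participation in the clinical investigation or the subject withdraws from the clinical investigation".

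**Stroke classification.** Appendix II calls a stroke disabling if there is "an mRS score of 2 or more at 90 days and an increase of at least one mRS category" over the pre-stroke baseline. It is non-disabling if there is "an mRS score of < 2 at 90 days" or no such increase. Both classes therefore use the 90-day score. Section 6.5.3.1 supplies it: after a TIA, stroke or encephalopathy, "further evaluation should be performed at an unscheduled visit 90 days" (± 14 days) from the event, with mRS, NIHSS and a neurological examination. It does not limit this to implanted subjects. Section 3.4.4 adds: "Events related to primary and descriptive endpoint criteria will be adjudicated according to the Valve Academic Research Consortium (VARC-2) definitions".

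**Use.** Protocol 4.2 and SAP 1.4.2 place disabling stroke, non-disabling stroke and a composite containing disabling stroke, all at 30 days, in the CE Mark submission.

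**Overall follow-up.** Section 3.3 says, without exception, that enrolled subjects are followed to the 12-month visit.

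**The concern.** The study exists to characterise the safety of a delivery system, and Attempted-to-Treat subjects are those in whom the delivery system was used and the valve was not implanted. If such a subject has a stroke, one set of sections ends follow-up before the score that defines the endpoint is due, while 6.5.3.1 still calls for it. A site cannot satisfy both. If it follows the withdrawal rule, the stroke has to be left unclassified or classified by a rule that the visible text does not give. In a single-arm study, a rule chosen once the event is known is open to challenge.

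The conflict with 3.3 is simpler. Because 5.4 itself classes these subjects as enrolled, 3.3 and 5.4 cannot both be right.

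**Working it through.** The plan gives no figure of its own to reproduce here. The check is day arithmetic from the protocol's windows, followed by an indication of scale.

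**1. Timing.** Day 0 is the index procedure.

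- Latest 30-day visit (6.5.2.1): 30 + 21 = day 51.
- mRS window for a stroke on day *d* (6.5.3.1): from *d* + 90 − 14 = *d* + 76 to *d* + 90 + 14 = *d* + 104.

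| Stroke on | mRS window | Shortfall from day 51 | Shortfall from day 30 |
|---|---|---|---|
| day 0 | 76 to 104 | 76 − 51 = 25 days | 76 − 30 = 46 days |
| day 30 | 106 to 134 | 106 − 51 = 55 days | 106 − 30 = 76 days |

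The window opens within follow-up for none of the 31 possible stroke days (0 to 30), even when every window is read in the plan's favour.

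**2. Does other visible text supply the score?**

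- The 30-day visit includes an mRS (6.5.2.1), but nothing lets it replace the 90-day score.
- Section 3.4.6 asks withdrawn subjects to agree to a call once the last subject has completed 12 months. That is not timed to the event. Section 3.4.7 requires a certified mRS assessor, and 6.5.3.1 an examination by a neurologist or neurology fellow.
- The permission clause in 5.5 covers only withdrawals for device safety or performance problems, and that follow-up lies outside the investigation.

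**3. Frequency.** The documents give no rates, so these are assumptions: a proportion *f* = 1% to 5% attempted but not implanted, and a 30-day stroke risk *s* = 2% to 10% among them. Expected cases = *n·f·s*; chance of at least one = 1 − (1 − *f·s*)^*n*.

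| *n* | *f* = 1%, *s* = 2% | *f* = 5%, *s* = 5% | *f* = 5%, *s* = 10% |
|---|---|---|---|
| 73 | 0.015 expected; 1.4% | 0.18; 16.7% | 0.365; 30.6% |
| 200 | 0.04 expected; 3.9% | 0.50; 39.4% | 1.0; 63.3% |

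**4. Effect of one case.** With exact Clopper-Pearson 95% intervals, the method named in SAP 2.2.2:

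- *n* = 73: 0/73 = 0% (0 to 4.93) against 1/73 = 1.37% (0.03 to 7.40), a shift of 1.4 points.
- *n* = 200: 0/200 = 0% (0 to 1.83) against 1/200 = 0.50% (0.01 to 2.75), a shift of 0.5 points.

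The composite shifts by the same amount only if the subject has no other component.

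**The case against.** **The visit may survive.** A reader might infer that the 90-day assessment is certainly lost. The documents do not show that. Section 6.5.3.1 is the event-specific rule and is not limited to implanted subjects, and the 30-day-only wording in 6.5.2 stands among the scheduled visits, not the unscheduled ones. A site could hold the visit on that reading. This stands as an objection to certainty, but it does not remove the problem: 5.4 and 6.2.3 still withdraw the subject, and 5.5 still stops data recording. What is shown is a conflict.

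**A rule may exist in text not available.** Protocol section 8 refers missing data and descriptive-endpoint analysis to the SAP. Protocol 8.8 and SAP 2.9 have no visible text, and the CEC works under a separate charter. Any of these could cover a missing 90-day mRS. This stands, and it lowers confidence that there is no classification route.

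**Analysis population.** A reader might also infer from 5.4, which states membership for Implanted and CIP Deviation subjects only, that Attempted-to-Treat subjects are left out of the analysis. The documents do not support this. Protocol 3.2 and SAP 1.3 count implant attempts, and SAP 3.2 summarises events for all enrolled subjects. The sections that would define the population (protocol 8.1 and 8.2.1.2, SAP 2.1) have no visible text.

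**Scale.** The upper frequencies need an assumed 10% stroke risk, and SAP 1.3 ties the CE Mark summary to the first 73 attempts, so the figures for 200 matter less. The affected endpoints are descriptive, and the composite already captures a fatal stroke within 30 days through mortality. All of this stands. The 3.3 conflict is one overview sentence against three specific sections that agree; it is real but editorial.

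**Conclusion.** The sections conflict and should be reconciled. Followed as written, the withdrawal rule ends follow-up at least 25 days before the score that defines both stroke classes can be obtained, so a stroke within 30 days of a failed implant could not be classified as Appendix II requires. Section 3.3 contradicts the same rule.

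The expected numerical effect is small: at most about 0.4 such strokes in 73 subjects under the assumed rates, each worth 1.4 points. The primary endpoint does not use the mRS and is unaffected. The stroke itself would still be reported as an adverse event under SAP 3.2; what is at risk is its class. Confidence is high that the passages conflict and moderate that no classification route exists, given the text that cannot be seen. No error in the analysis population is shown.

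**What to change.** 1. Check whether protocol 8.8, SAP 2.9 or the CEC charter already says how a stroke without a 90-day mRS is classified. If so, refer to that rule in 5.4.
2. Reconcile 3.3, 5.4, 5.5, 6.2.3 and 6.5.2 with 6.5.3.1. The most direct way is to state that the day-30 withdrawal does not apply to the 90-day neurological assessment of a subject who had a neurological event within 30 days, and that its data are recorded.
3. Failing that, state in advance how such strokes are classified, for example reported as unclassified with the disabling-stroke, non-disabling-stroke and composite rates shown both ways.
4. Give 3.3 an exception for Attempted-to-Treat subjects, or otherwise bring it into line with 5.4.
5. Confirm that protocol 8.1, 8.2.1.2 and SAP 2.1 match the attempt-based wording of protocol 3.2 and SAP 1.3.

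Cost: a few sentences, plus ethics committee approval of the amendment and any consent-form change (protocol 10.3 and 12.1) at up to eight sites. Under the assumed rates, keeping the assessment adds at most about one stroke visit over 200 subjects (200 × 0.05 × 0.10 = 1.0), and somewhat more if TIA and encephalopathy, which 6.5.3.1 also covers, are counted.
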